המרכז הרפואי תל-אביב
ע"ש סוראסקי
רפואה מובילה ואנושית

Proposed Study Title

Study Title

Performance Evaluation Protocol for Sight Diagnostics' OLO CBC Analyzer by Ichilov oncology daily care center.

Contact Information

Name

[name]

Job Title

VP R&D

Institution

Sight Diagnostics

Address 1

[name]

Address 2

City, State, Zip

Tel Aviv

Country

Israel

Phone/Fax

E-mail	[contact]
--------	--------------------

Study Information

Tumor Type	N/A				
Areas of Interest	N/A				
# of Patients	50	Study Duration (Months)	1	Number of Sites	1
Site Names	Sight Diagnostics				

Hypothesis / Overall Objectives

Background:

The Sight OLO is a quantitative multi-parameter automated hematology analyzer intended for in vitro diagnostic use in screening capillary or venous whole blood samples collected in K₂EDTA blood collection tubes, or fingertip samples collected using the Sight OLO test kit microcapillary tubes. When used with the Sight OLO cartridge, the Sight OLO enumerates the following CBC parameters in whole blood: WBC, RBC, HGB, HCT, MCV, MCH, MCHC, RDW, PLT, NEUT%/#, LYMPH %/#, MONO %/#, EOS%/#, and BASO%/#.

The Sight OLO is indicated for use in point of care and clinical laboratories to identify and classify one or more of the formed elements of blood in children 3 months and above, adolescents and adults. In case a different intended use is required by the evaluating site, Sight should be informed in advance.

As there are great benefits in performing CBC tests from fingertip in oncologic patients, this study aims to establish OLO’s performance accuracy of CBC results for finger prick samples across the OLO reportable range, and particularly around relevant medical decision points. Additionally, the study will evaluate OLO’s compatibility to Ichilov oncology daily care center, while focusing on its effect of workflow and turnaround time.

Hypothesis:

The results of this study are expected to show good performance of OLO and its equivalence to the site's standard hematology system - Beckman Coulter DxH800 analyzer - in samples spanned over a wide clinical measuring range and covering medical decision points for WBC, HGB, PLT, and NEUT#. The medical decisions taken for treating chemotherapy patients at the oncology center are expected to remain equal when based on the results given by Sight OLO.

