OLO is hypothesized to allow shorter time to CBC results, by minimizing the time period from phlebotomy to results, currently prolonged due to the need to send blood samples from the oncology

daily care center to the central lab. By that, Sight OLO would improve workflow efficiency and provide care to patients in a reliable and accelerated fashion.

Study Description

Provide a concise overview stating the type of study, phase, design, and compounds

Study design:

This evaluation will include two studies:

1. A matrix study will compare a capillary sample collected via finger prick with a venous sample collected into a blood tube, both scanned on OLO.
2. A method comparison study will compare Sight OLO to Beckman Coulter DxH800 using a venous sample collected into a blood tube.

During a period of 2 weeks, approximately 50 whole blood samples will be collected from patients at the oncology daily care center.

Patient Enrollment:

- Each patient participating in the study will firstly fill and sign an Informed Consent Form (ICF). Subjects participating in the study will be rewarded with a coupon for coffee and cake.
- For de-identification purposes, study barcode stickers will be used for all of OLO scans, instead of the original patient identification details. An unblinded form will be used to match the de-identification barcode with the patient identification details (this form will remain at the center and will not be shared externally).
- Patient enrollment will be documented in a designated worksheet, using the study barcode stickers.
- The patient will be asked to rest for at least 15 minutes.

Phlebotomy and Scanning Flow:

During the routine blood collection, an additional venous sample will be collected in K₃EDTA tube as part of the study. The phlebotomy time will be recorded in the worksheet.

The first tube will get a study barcode sticker and remain in the daily care center at a room temperature of 18°C-26°C. The second tube will be sent to the lab to be scanned on Beckman Coulter DxH800, as part of the routine procedure.

Two consecutive finger prick samples will be collected from the 3rd and 4th fingers of the patient's non-dominant hand (in this order) and scanned on OLO, and the time of the first result will be recorded in the study worksheet.

Following two successful finger prick scans, the venous sample (collected previously for the study) will be scanned on OLO.

The following time points will be recorded in the study worksheet:

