Once all the predefined range groups are covered, the study will be completed and the results will be analyzed.

Statistical considerations:

Passing Bablok regression analyses will be performed for each measurand between:

- (1) The mean value given by OLO for the finger prick samples and the value given by OLO for the venous sample.

- (2) The value given by OLO for the venous sample and the value given by Beckman Coulter DxH800 for the venous sample.

Measurands invalidated by either OLO or Beckman Coulter DxH800 will be removed from all analyses.

The time to result will be compared between the time of first available finger prick results (from the scan on OLO) and the time of available venous results (from the routine scan on Beckman Coulter).

After study completion, medical records of the enrolled patients will be reviewed to evaluate whether the same clinical decision would have been taken when based on OLO results.

Environmental requirements:

- OLO should be placed on a stable bench (shared with no vibrating equipment) with enough space for the device and an adjacent surface for sample preparation. OLO's physical measurements are: 25.7X32.6X28.7 cm, 10 kg.
- Power supply - OLO is provided with a power supply unit which needs to be connected to a standard grounded power socket.
- Internet connectivity - not mandatory for operation but preferable for remote support and monitoring. LAN connectivity is preferable. Sight can provide 3G/4G dongle for cellular connectivity. It would be best to contact an IT person directly to understand whether there are special compliance requirements when connecting OLO to the local network/internet.
- Each blood tube should be kept at room temperature of 18°C-26°C throughout the day until the last scan is completed. The OLO operating temperature range is 18°C-30°C, relative humidity range is 20%-80%.
- The reference device must be calibrated and approved for use according to the lab standard operating procedures during the entire performance evaluation study. If any calibration process is performed during the study, Sight should be informed, preferably in advance, to be able to take the steps required to avoid interference with the method comparison (such as the removal of the samples scanned before/after the calibration).
- Results from the OLO can be exported as a CSV file through a USB drive and sent via email.

Sharing of results:

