- Given this is an early comparison study, results will be shared openly across both parties.
- CSV files with the results of OLO and de-identified PDF files with the results of the reference device should be shared regularly by the study coordinator.
- Study worksheets and enrollment forms will be delivered once completely filled.

Study Population

Brief description, setting and key inclusion/exclusion criteria

Inclusion Criteria:

Blood samples will be collected from oncologic patients older than 18 years old arriving at the oncologic daily care center of Ichilov hospital.

The sampling method will initially be randomized, though will aim to include both normal and abnormal ranges of blood counts (according to Beckman Coulter DxH800 as the reference analyzer), while covering wide analytical ranges with balanced distributions, focusing on values around medical decision points. Approximately 30 abnormal samples will be collected, with the ranges to cover specified in table 1 below. Note that a single sample can cover multiple ranges for different parameters. Additionally, approximately 20 normal samples will be collected, while for the purpose of this protocol, normal is defined as samples with values above the ranges specified in table 1 for all parameters (PLT>100X10³/μL, HGB>12.0g/dL, WBC>4.0X10³/μL, NEUT#>2.0X10³/μL), and with no flags on the site reference analyzer.

Table 1 - abnormal ranges

[figure not shown]
	Range	# of paired samples
PLT	<100X10 ³ /μL and >50X10 ³ /μL	2
	<50X10 ³ /μL and >30X10 ³ /μL	4
	<30X10 ³ /μL and >18X10 ³ /μL	4
	<18X10 ³ /μL	4
HGB	<12.0g/dL and >10.0g/dL	4
	<10.0g/dL and >4.0g/dL	4
WBC	<4.0X10 ³ /μL and >2.0X10 ³ /μL	2
	<2.0X10 ³ /μL	7
NEUT#	<2.0X10 ³ /μL and >1.0X10 ³ /μL	3
	<1.0X10 ³ /μL and >0.5X10 ³ /μL	3
	<0.5X10 ³ /μL	2

Exclusion Criteria:

- Visibly hemolyzed specimens (sample plasma should be checked for hemolysis by technician while selection of specimen from tube racks).
- Visibly clotted specimens (Reasonable to assume that samples processed with clinical reported results are not clotted).
- A sample that is not successfully scanned on OLO within 3 attempts (e.g. rejected due to irregular cell morphology, or microscopically visible hemolysis).

Study Schema

Please insert a graphic study schema or visual representation of trial design

Protocol revision signatures: This study protocol has been reviewed by Sight's key personnel with their signature approval for its use.

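### The clinical-decision review states no masking and does not name the OLO result it uses, so agreement is at risk of upward bias and is not uniquely defined

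*Protocol*

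**What the plan says.** Under Hypothesis, the protocol predicts that chemotherapy treatment decisions "are expected to remain equal when based on the results given by Sight OLO". The only analysis of that prediction is the last sentence of Statistical considerations: once the study is complete, "medical records of the enrolled patients will be reviewed to evaluate whether the same clinical decision would have been taken" on the strength of OLO results.

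Under Phlebotomy and Scanning Flow, routine care runs on the reference analyser: "The second tube will be sent to the lab to be scanned on Beckman Coulter DxH800, as part of the routine procedure". For OLO, "Two consecutive finger prick samples will be collected from the 3rd and 4th fingers", and afterwards "the venous sample (collected previously for the study) will be scanned on OLO". Each patient therefore has three OLO results.

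The other analyses in Statistical considerations each name the OLO value they use: the mean of the two pricks, the venous scan, or, for timing, the first prick ("The time to result will be compared between the time of first available finger prick results"). The decision review does not. It also gives no reviewer, no masking and no rule for calling two decisions the same.

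**The concern.** There are two separate problems.

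**Anchoring.** To ask whether OLO would have led to the same decision, the reviewer needs the decision already taken, and the only source named is the medical record. Read plainly, someone who can see the outcome judges whether a second set of counts would have changed it. That is not an independent second decision, and the likely pull is towards agreement.

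**Undefined comparison.** With three OLO results per patient and none named, the agreement figure depends on a choice that can be made after the data are seen. The result that delivers the time saving is the first finger prick. Agreement computed on the mean or on the venous scan would describe a different result from the one that is faster.

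This matters because the two planned regressions do not fill the gap. One compares finger prick with venous blood, both on OLO. The other compares OLO with DxH800, both on venous blood. Neither sets a finger prick directly against DxH800. The decision review is the only planned comparison of results, as opposed to timing, in which that could happen.

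**Working it through.** **1. What the protocol fixes for each analysis**

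| Analysis (Statistical considerations) | OLO value | Comparator |
|---|---|---|
| Regression 1 | mean of two finger pricks | OLO venous |
| Regression 2 | venous | DxH800 venous |
| Time to result | first available finger prick | routine DxH800 result |
| Decision review | not named | decision in the record |

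The protocol gives no target, margin, discordance rate or measurement error for decision agreement, so there is no figure to reproduce. Steps 2 and 3 are illustrations on assumed inputs.

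**2. Anchoring**

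From Inclusion Criteria: about 30 abnormal and 20 normal samples (30 + 20 = 50). Assume that decisions always agree in normal samples and truly agree with probability p in abnormal samples, and that the reviewer keeps the recorded decision in a share a of truly discordant cases. Observed agreement = [20 + 30 × (p + (1 − p)a)] / 50.

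| p | a = 0 | a = 0.25 | a = 0.50 |
|---|---|---|---|
| 0.80 | (20 + 24)/50 = 88% | (20 + 25.5)/50 = 91% | (20 + 27)/50 = 94% |
| 0.90 | (20 + 27)/50 = 94% | (20 + 27.75)/50 = 95.5% | (20 + 28.5)/50 = 97% |

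A simpler version: if 5 of 50 decisions truly differ, agreement is 45/50 = 90% (exact 95% CI 78% to 97%). If a share f of the 5 is hidden, expected agreement is 1 − 5(1 − f)/50, which is 92.5% at f = 0.25 and 95% at f = 0.50.

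**3. Choice of OLO result**

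Assume one cut-off, scaled to 1, and true values t uniform between 0.8 and 1.2. Each reading is t × (1 + CV × Z), with Z standard normal and independent, and no systematic offset between devices or sample types. CV is 3% for DxH800, 4% for OLO venous, and 5%, 10% or 15% for a finger prick. Agreement is the proportion of 400,000 simulated patients in whom the OLO value and DxH800 fall on the same side of the cut-off.

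| Finger-prick CV | First prick | Mean of two | Venous | Any one of the three |
|---|---|---|---|---|
| 5% | 88% | 91% | 90% | 98% |
| 10% | 80% | 85% | 90% | 98% |
| 15% | 73% | 79% | 90% | 98% |

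Relative to the first prick, the other choices move agreement by between about 2 points (90 − 88, venous at 5% CV) and about 25 points (98 − 73, any of three at 15% CV). A rule that all three must agree moves it the other way: with three independent results each agreeing 90% of the time, 0.9³ = 73%. These figures are for values within 20% of a cut-off, so agreement over all 50 samples would be higher.

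**The case against.** The strongest reply is that the sentence does not describe a biased procedure; it is simply short. It does not say who reviews, that the reviewer sees the recorded decision or the DxH800 values, or that one person makes both judgements. Someone could extract the recorded decision and compare it with one formed separately from OLO values, and that would fit the wording. This stands as a limit on the claim: the protocol shows a risk, not an established bias. It does not remove the point, because nothing requires the separate procedure and the plain reading is an open review. A later analysis plan cannot undo an unmasked review once it has been done.

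It can also be said that naming the replicate belongs in a statistical analysis plan, which may exist. This partly stands, and alone the omission would be minor. The protocol does name the value for each of its other analyses, however, and masking is a matter of study conduct.

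Three further limits also stand:

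- The intended use stated under Background covers venous and capillary tube samples as well as fingertip samples. The case for the first prick rests on the timing comparison and the finger-prick aim, not on the intended use.
- The statement under Sharing of results that "results will be shared openly across both parties" concerns data exchange between sponsor and site. It says nothing about what the decision reviewer sees.
- The evaluation is an early one built on two comparison studies, and the decision review is not listed as an endpoint.

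Finally, the assumed anchoring shift (90% to between 92.5% and 95%) lies inside the 78% to 97% interval. That is true, but the interval measures sampling error and would not reveal the shift.

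**Conclusion.** The point holds as a risk and an ambiguity. The only test of the decision hypothesis takes its comparator from records of care based on DxH800, states no masking, and leaves open which of three OLO results is used. Agreement is therefore exposed to anchoring, most plausibly upwards, and has no unique definition.

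A reader might infer that both gaps push agreement upwards, or that agreement is biased as a matter of fact. The protocol does not support either. Anchoring is likely, but its size cannot be derived. The unnamed OLO result has no direction of its own: agreement rises if the mean, the venous scan or any matching result is taken, and falls if all three must match.

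The sizes shown (3 to 6 points for anchoring at 80% true agreement in abnormal samples, that is 91 − 88 and 94 − 88; about 2 to 25 points for the choice of result) rest wholly on assumed discordance, anchoring and CV values. The two regressions and the time-to-result comparison are unaffected. This is an inexpensive improvement that should be made before the review is carried out.

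**What to change.** Replace the sentence on record review in Statistical considerations with text to this effect:

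- For each patient, the reviewer records a decision from the first accepted finger-prick OLO values, without seeing the DxH800 values or the recorded decision.
- The same reviewer separately records a decision from the DxH800 values, also without seeing the recorded decision.
- Cases are shuffled and carry no device name, and the two reads of one patient are kept apart.
- Paired agreement is reported with an exact 95% CI, overall and separately for the roughly 30 abnormal samples, because the roughly 20 normal samples may dilute disagreement.
- Agreement of the masked OLO decision with the recorded decision, and results based on the mean of two pricks or on the venous scan, are supportive.

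The first prick is chosen because it is the single result behind the time-to-result comparison. No clinical threshold is proposed.

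**Cost.** One protocol paragraph, preparation of case extracts with the recorded decision removed, and about 50 extra short reads after completion; no extra patients or procedures. Some inconsistency within the reviewer will be counted as disagreement between devices. Comparing the masked DxH800 decision with the recorded decision shows how much. Shuffling and spacing reduce, but cannot exclude, recognition of the same patient. The agreement figure may come out less favourable.
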